1.6.3.1 Participants' compliance

Participants were classified as non-compliant if they: (i) failed to wear the appliance for at least 22 hours daily, (ii) experienced appliance breakage more than three times (as reported during follow-up visit), or (iii) demonstrated insufficient clinical progress, defined as <10% reduction in overjet after six months of appliance wear.

Non-compliant participants were managed according to the intention-to-treat protocol and continued treatment as appropriate, either with a fixed functional appliance or by monitoring until growth cessation for subsequent fixed appliance therapy. Participants who demonstrated non-compliance during the study period were identified and classified accordingly; however, in accordance with the intention-to-treat principle, their data were retained in the final analysis. All available outcome data up to the point at which non-compliance was identified were included to preserve the original group allocation and minimise attrition bias. This approach ensures that the analysis more accurately reflects real-world clinical conditions and maintains the validity of the treatment effect estimates.

In cases of appliance loss, a replacement appliance was fabricated at the participant's expense. This policy was explained to participants and parents during the consent process. All appliance losses and breakages were documented. In this study, all participants were compliant with the treatment, and only one participant in the Twin Block was recorded as a dropout due to missing as participant cannot be contacted even though multiple attempts were made.

1.7 Post-advancement phase (T1)

General inclusion criteria required that cases treated with MAA to continue their treatment according to the prescribed aligner treatment plan. In contrast, cases treated with Twin Block appliances subsequently progressed to Phase 2, which involved comprehensive fixed appliance therapy.

Immediately after participants met the completion criteria, intra-oral scans and extra-oral/intra-oral photographs were obtained. Participants were then referred to the Radiographic Unit, Faculty of Dentistry, Universiti Malaya, for lateral cephalometric radiographs, taken with the same machine as the pre-treatment records at a 1:1 magnification scale. Participants subsequently completed the questionnaire (Appendix D and Appendix E).

1.8 Intention to treat

The study adopted an Intention-to-Treat (ITT) approach to preserve the validity of its findings. In accordance with ITT principles, all enrolled participants were included in the final

analysis regardless of treatment completion. This maintained the randomised nature of the trial, minimised selection bias, and reflected real-world clinical conditions.

The ITT analysis accounted for non-compliance, dropouts, and protocol deviations, thereby providing a comprehensive evaluation of the effectiveness of mandibular advancement aligners with and without vertical bite opening, and the Twin Block appliance in Class II malocclusion growth modification.

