1.6.3 Follow-up visits

Participants were scheduled for monthly follow-up appointments. At each visit, assessments were conducted by the principal investigator ([name]) under orthodontic supervision. Clinical records included overjet, overbite, incisor, canine, and molar relationships. Appliance condition was also evaluated for objective signs of wear, such as surface dullness or loss of shine, to assess compliance.

Follow-up intervals were adjusted as needed until at least to a Class I molar relationship and/or edge-to-edge incisal contact were achieved. Participants who failed to meet these criteria despite continued mandibular advancement therapy were classified as non-compliant, and records were taken for final data analysis.

To enhance compliance, participants were provided with a diary to record their daily appliance wear and experiences. These entries were reviewed and discussed with the investigator at follow-up visits, focusing on duration and consistency of wear.

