1.10.1 Statistical Tests

For all statistical tests, the level of significance was set at $p\text{-value} < 0.05$ with a 95% confidence interval. In addition, results with $p\text{-value} < 0.001$ were considered highly significant to further emphasise the strength of these findings.

For within-group comparisons of skeletal, dentoalveolar, and soft tissue changes between the pre-treatment phase (T0) and immediately after the advancement phase (T1), paired t-tests were performed for all the normally distributed data, and for between-group comparisons of skeletal, dentoalveolar, and soft tissue changes, one-way ANOVA was employed.

For assessment of participants' perceptions, responses to the questionnaire were recorded as follows: "never" = 1, "hardly ever" = 2, "sometimes" = 3, "fairly often" = 4, and "very often" = 5. Total scores were computed and compared between pre- and post-intervention using paired t-tests. One-way ANOVA was employed for comparisons between intervention and control groups.

For intra-rater and inter-rater reliability, the Intra-class Correlation Coefficients (ICC) score was employed to assess the reliability and accuracy of the measurement. The ICC score was interpreted according to Koo & Li (2016).

Table 3.11 Statistical analysis of this study

Objectives	Variables	Statistics
Objective 1	Changes in the skeletal effects at pre- and post-intervention: SNA (°), SNB (°), ANB (°), Wit's analysis (mm), Co-Gn (mm), SN-Maxillary Plane (°), SN-Mandibular Plane (°), Maxillary-Mandibular Plane (°)	Paired t-test
Objective 1	Changes in the skeletal effects of the three groups: SNA (°), SNB (°), ANB (°), Wit's analysis (mm), Co-Gn (mm), SN-	ANOVA test

	Maxillary Plane (°), SN-Mandibular Plane (°), Maxillary-Mandibular Plane (°)	
Objective 2	Changes in the dentoalveolar effects at pre- and post-intervention: Overjet (mm), Overbite (%), Upper incisor angle (°), Lower incisor angle (°), Inter-incisor angle (°)	Paired t-test
Objective 2	Changes in the dentoalveolar effects of the three groups: Overjet (mm), Overbite (%), Upper incisor angle (°), Lower incisor angle (°), Inter-incisor angle (°)	ANOVA test
Objective 3	Changes in the soft tissue effects at pre- and post-intervention: Upper lip-E-line (mm), Lower lip-E-line (mm), Nasolabial angle (°).	Paired t-test

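### The plan reports an intention-to-treat analysis of everyone enrolled, but its tests can use only participants with both T0 and T1, one Twin Block participant dropped out, and the data rules for non-compliers conflict.

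*Combined protocol and SAP*

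**What the plan says.** **Analysis set.** Section 1.8 (Intention to treat) states that "all enrolled participants were included in the final" analysis, whether or not treatment was completed. It adds: "The ITT analysis accounted for non-compliance, dropouts, and protocol deviations". No technique is attached to that statement.

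**Tests.** Section 1.10.1 (Statistical Tests) says that "paired t-tests were performed for all the normally distributed data" for T0 to T1 within groups, and that one-way ANOVA was used for changes between groups. Table 3.11 repeats this pairing for all four objectives, including the questionnaire.

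**Time points.** The questionnaire is given at T0 and T1 only (Section 1.6.1). Lateral cephalograms are described at pre-treatment (Section 1.5.6) and post-advancement (Section 1.7) only.

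**What happened.** Section 1.6.3.1 (Participants' compliance) reports: "In this study, all participants were compliant with the treatment". The same sentence says that "only one participant in the Twin Block was recorded as a dropout", because this person could not be reached.

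**Non-compliers.** Section 1.6.3.1 says that "All available outcome data up to the point at which non-compliance was identified were included". Section 1.6.3 (Follow-up visits) says that participants who did not reach the end-point "were classified as non-compliant, and records were taken for final data analysis". Section 1.7 has T1 records taken once the completion criteria are met.

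**The concern.** A reader of Section 1.8 would conclude that every randomised participant contributes to every comparison and that the missing data were dealt with. The methods show neither. A paired t-test or an ANOVA on change has nothing to work on when T1 is absent, so the participant drops out of the calculation without comment.

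The loss falls in the sole control arm, which enters every comparison with an aligner. With seven planned per arm, one participant is a noticeable share, and nothing in the plan tests whether the result depends on that person.

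The second issue is the rule for non-compliers. T0 and T1 are the only analysed time points. Read literally, keeping data only until non-compliance is identified would leave someone identified before T1 with T0 alone, and the tests would then omit that person too. Non-compliance is also partly defined by outcome: not reaching the end-point (Section 1.6.3), or less than 10% reduction in overjet after six months (Section 1.6.3.1). Overjet is itself an analysed outcome. A cut-off tied to that label could selectively lose poor responders, which an intention-to-treat analysis is meant to prevent.

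**Working it through.** **Inputs.** From Section 1.2.2: 5 per group, raised by 30% to 7 per group, 21 in total. From Section 1.6.3.1: one Twin Block dropout and no non-compliers. Assumptions: 7 per arm were actually randomised (the text gives only the planned figure), and the dropout has T0 but no T1.

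**1. Planned number.** 5 x 1.3 = 6.5, rounded up to 7; 7 x 3 = 21. The plan's figure is reproduced.

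**2. Number the tests can use.** Overall 21 - 1 = 20, so 1/21 = 4.8% is missing. In Twin Block 7 - 1 = 6, so 1/7 = 14.3% is missing. The arms analysed are 7, 7 and 6.

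**3. Possible shift in the Twin Block mean.** Let m be the mean change in the six observed participants, and let the missing change be m + k SD. The mean of all seven is (6m + m + k SD)/7 = m + (k/7) SD.

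| k (assumed) | Shift in the mean |
|---|---|
| 1 | 0.14 SD |
| 2 | 0.29 SD |
| 3 | 0.43 SD |

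**4. Yardstick.** The standard error of a 6 v 7 difference is sqrt(1/6 + 1/7) = sqrt(0.3095) = 0.56 SD. For k = 1 to 2 the shift is 0.14/0.56 to 0.29/0.56, about a quarter to a half of a standard error.

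**5. Power.** The text gives no SD for the effect size of 1.83, so it is read here as a standardised difference (an assumption). With a two-sided t-test at 0.05, power for Twin Block against one aligner arm is 0.881 at 7 v 7 and 0.849 at 6 v 7. For the three-arm ANOVA with only Twin Block differing, it is 0.911 at 7, 7, 7 and 0.875 at 7, 7, 6. The loss is small.

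**6. Non-complier rules side by side.**

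| Section | Data from a non-complier |
|---|---|
| 1.6.3 | Records taken for the final analysis |
| 1.6.3.1, preceding sentence | Data kept in the final analysis |
| 1.6.3.1, cut-off sentence | Data only until non-compliance is identified |
| 1.7 | T1 follows once the completion criteria are met; no T1 timing for those who do not meet them |

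These cannot all be applied to the same person without a further rule on when T1 is taken. The number affected in this trial, as reported, is 0.

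**The case against.** The strongest reply is that the plan does follow the intention-to-treat principle where it counts. Participants stay in their assigned arm, Section 1.6.3 takes final records from those who fail the end-point, and Section 1.6.3.1 says their data are retained. On a natural reading, T1 records are taken when failure is declared, so the non-complier has a change score. Nobody was reported as non-compliant, so the cut-off sentence removed no one. The single loss was a failure of contact, the shift in step 3 rests on an assumed 1 to 2 SD, and power hardly changes.

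Most of this stands, and it limits what can be said. A reader might infer that the plan is a completer analysis that discards treatment failures. The documents do not support that: two statements keep non-compliers in, one sentence points the other way, and the result is a contradiction rather than an exclusion rule. A reader might also infer that the Twin Block dropout left because the appliance failed. No section links the two.

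What the reply does not answer is the dropout. Retention in the assigned arm does not create a T1 value. Monthly overjet and overbite are recorded (Section 1.6.3), but no analysis of interim values is specified, so they do not fill the gap. The statement that everyone enrolled was analysed, with dropouts accounted for, remains one that the named tests cannot deliver.

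**Conclusion.** The point holds in two parts of unequal weight.

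First, the stated analysis set is wrong as written. The methods give a complete-case analysis by assigned arm, with at most 20 of a planned 21 and 6 of 7 in Twin Block. The numerical consequence is probably modest: 0.14 to 0.29 SD in the Twin Block mean if the missing change is 1 to 2 SD away, about half a standard error or less. Its direction is unknown. The size rests on that assumed departure, on 7 per arm randomised, and on the dropout having no T1. The mismatch between label and tests rests only on there being no T1 for the dropout.

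Second, the rules on data from non-compliers conflict and need reconciling. Because no participant was reported as non-compliant, this is a defect in the text and not a bias that has occurred in this trial.

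**What to change.** 1. In Section 1.8, describe the analysis as available-case by randomised arm, state the number randomised and analysed in each arm, and say that the Twin Block dropout has no T1 (if so).
2. Add a best/worst-case sensitivity check in Section 1.10.1: repeat the between-group comparison with the dropout given the largest, then the smallest, observed Twin Block change.
3. Delete the sentence in Section 1.6.3.1 that stops data at the identification of non-compliance. State that any T1 record is analysed in the randomised arm whatever the compliance.
4. Reconcile Sections 1.6.3, 1.6.3.1 and 1.7 on when T1 is recorded for participants who do not meet the completion criteria.
5. Report failure to reach the end-point by arm, so that it is visible as a result and not only as a compliance label.

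A mixed model that takes in the dropout's T0 is not needed. With two time points it would allow n = 21 to be written but would add almost nothing on change.

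The cost is SAP wording and one extra sensitivity run, with no new data. The price is a slightly less favourable statement of the analysis set.

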1.9.1 Tracing method

Lateral cephalometric analysis was performed using a semi-manual tracing method with AI-powered WebCeph software (AssembleCircle Corp, Korea). All radiographs were first uploaded as randomised and anonymised files via Google Drive. They were then calibrated for magnification within the WebCeph software to ensure a 1:1 scale prior to landmark identification and analysis. Tracing was carried out on the same computer system under standardised conditions.

Each cephalogram was labelled with 13 hard tissue landmarks (S, N, ANS, PNS, Point A, Ui, Li, upper incisor root apex, lower incisor root apex, Point B, Menton, Gonion, Condylion) and 4 soft tissue landmarks (Pogonion, Pronasale, Labrale Superius, Labrale Inferius) as illustrated in Figure 3.15. Landmarks were initially identified using the software's AI digitisation function, with manual corrections applied when necessary. Lines, planes, and angular measurements were generated using a modified cephalometric analysis protocol incorporating parameters from Steiner, Downs, McNamara, Tweed, and Jacobson (Wit's) analysis. Data were tabulated for subsequent statistical analysis.

[figure not shown]

Figure 3.15 Landmarks of lateral cephalometric analysis

1.9.2 Lateral cephalometric parameters

The lateral cephalometric parameters selected for analysis were determined in accordance with the anticipated biological and clinical effects of the respective interventions. For clarity and systematic evaluation, these parameters were categorised into three effects: skeletal effects, dentoalveolar effects, and soft tissue effects. This classification facilitated targeted assessment of treatment outcomes corresponding to each anatomical component influenced by mandibular advancement treatment. The full list of parameters and their operational definitions is presented in Table 3.7. To enhance conceptual understanding, the parameters are also visually illustrated according to their respective categories in Figure 3.16 (Skeletal Effects), Figure 3.17 (Dentoalveolar Effects), and Figure 3.18 (Soft Tissue Effects).

Table 3.7 Definitions of lateral cephalometric parameters

Parameters	Definitions
	SNA (°): The SNA angle is formed by connecting the sella, nasion, and A-point.
	SNB (°): The SNB angle is formed between sella, nasion and point B
	ANB (°): The ANB angle evaluates the anteroposterior relationship between the maxilla and mandible. The angle formed between point A, nasion and point B

Skeletal Effects

Parameters

Wit's Analysis (mm): *Drawn perpendiculars from points A and B onto the occlusal plane and measured the distance between these two points*

Co-Gn (mm): *The distance between condylion and gonion*

SN-Maxillary Plane Angle (°): *The angle formed between the sella-nasion plane and maxillary plane.*

SN-Mandibular Plane Angle (°): *The angle formed between the sella-nasion plane and mandibular plane.*

Maxillary-Mandibular Plane Angle (°): *The angle formed between the maxillary plane and mandibular plane.*

Lower Anterior Facial Height (%): *The ratio of lower anterior facial height to the total face height.*

Overjet (mm): *The distance between the incisal ridges of the upper incisor teeth labially and the incisal ridges of the lower incisor teeth.*

Overbite (%): *Vertical (superior-inferior) overlap of the maxillary central incisors over the mandibular central incisors.*

Dentoalveolar Effects

Parameters

Upper incisal angle (°): *The angle between the long axis of the maxillary central incisor and the palatal plane.*

Lower incisal angle (°): *The angle between the long axis of the mandibular central incisor and the mandibular plane.*

Inter incisal angle (°): *The angle formed by the intersection of lines drawn through the long axis of the maxillary and mandibular incisors.*

Upper lip- E-line (mm): *The distance from the upper lip to Rickett's E-line.*

Lower lip- E-line (mm): *The distance from the lower lip to Rickett's E-line.*

Soft tissue Effects

Parameters

Nasolabial angle (°): *The angle formed by drawing a line tangent to the base of the nose and a line tangent to the upper lip.*

[figure not shown]

Figure 3.16 Skeletal Effects Parameters

[figure not shown]

Figure 3.17 Dentoalveolar Effects Parameters

[figure not shown]

Figure 3.18 Soft Tissue Effects Parameters

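### The outcome labelled Co-Gn is defined as condylion to gonion, and gnathion is not among the listed landmarks, so label, definition and landmark list must be reconciled

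*Combined protocol and SAP*

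**What the plan says.** Section 1.9.2 gives Table 3.7 the status of a specification: "The full list of parameters and their operational definitions is presented in Table 3.7". In that table the skeletal parameter labelled Co-Gn (mm) is "The distance between condylion and gonion".

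Section 1.9.1 states which points were labelled on each cephalogram: "13 hard tissue landmarks (S, N, ANS, PNS, Point A, Ui, Li, upper incisor root apex, lower incisor root apex, Point B, Menton, Gonion, Condylion"), followed by "4 soft tissue landmarks (Pogonion, Pronasale, Labrale Superius, Labrale Inferius"). Landmarks were first placed by the software and corrected by hand where needed. The same section adds: "Lines, planes, and angular measurements were generated using a modified cephalometric analysis protocol", drawing on several published analyses, the Wits analysis among them.

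Table 3.11 (section 1.10.1) carries Co-Gn forward by label only, under Objective 1. It is tested by paired t-test for pre- to post-treatment change and by ANOVA between the three groups.

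For Wits, Table 3.7 says: "Drawn perpendiculars from points A and B onto the occlusal plane and measured the distance between these two points". The text does not say which points define that plane.

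**The concern.** The abbreviation and the definition point to two different distances, and the landmark list sides with the definition. That makes it hard to dismiss as one mistyped word: a reader who follows sections 1.9.1 and 1.9.2 literally can compute Condylion-Gonion and cannot compute condylion-gnathion.

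Results tables will carry the label. Most readers will take Co-Gn as condylion-gnathion, a length that spans both the ramus and the body of the mandible. If the figures are Condylion-Gonion, any difference, or absence of one, between the two aligner groups and the Twin Block group would be attributed to the wrong dimension. The reliability exercise in section 1.9.3 would not reveal this. Two tracers measuring the same wrong distance consistently would still obtain a high intra-class correlation.

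**Working it through.** **1. Is the landmark list complete as printed?** Section 1.9.1 states 13 hard-tissue and 4 soft-tissue points. Counting the names:

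- Hard tissue: S, N, ANS, PNS, A, Ui, Li, upper incisor apex, lower incisor apex, B, Menton, Gonion, Condylion = 13.
- Soft tissue: Pogonion, Pronasale, Labrale Superius, Labrale Inferius = 4.

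Both counts match the stated figures, so gnathion was not lost when the text was extracted.

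**2. Which distance can be built from the list?**

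| Reading of Co-Gn | Points needed | In the list? |
|---|---|---|
| As labelled (standard notation) | Condylion, Gnathion | Gnathion absent |
| As defined in Table 3.7 | Condylion, Gonion | Both present |

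Menton is listed, but it is a separate landmark and neither the label nor the definition refers to it.

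**3. Can one distance stand in for the other?** In the triangle Condylion-Gonion-Gnathion, with g the angle at gonion, the law of cosines gives

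CoGn² = CoGo² + GoGn² − 2 × CoGo × GoGn × cos(g).

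The documents give no values for these lengths, so I set CoGo = 1 and use illustrative assumptions: GoGn from 1.0 to 1.4 and g from 110° to 130°.

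| GoGn | g = 110° | g = 120° | g = 130° |
|---|---|---|---|
| 1.0 | 1.638 | 1.732 | 1.813 |
| 1.2 | 1.806 | 1.908 | 1.996 |
| 1.4 | 1.979 | 2.088 | 2.182 |

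Condylion-Gonion equals 1 in every cell, while condylion-gnathion runs from 1.64 to 2.18. For example, at 120°, lengthening the body from 1.0 to 1.2 moves condylion-gnathion from 1.732 to 1.908, a rise of 0.176/1.732 = 10.2%, and moves Condylion-Gonion by nothing. The step is exaggerated for illustration. The point is that one measure is blind to body length and gonial angle and the other is not.

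**4. How much of the analysis is touched?** Table 3.11 lists 8 skeletal, 5 dentoalveolar and 3 soft-tissue outcomes: 8 + 5 + 3 = 16. Co-Gn is one of the 16 and one of the 8.

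**5. Wits.** The only tooth-crown points listed are the incisor tips, Ui and Li. No molar or premolar point is listed, so the posterior end of the occlusal plane is not specified in the text.

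**The case against.** The strongest reply is that the list need not be exhaustive of what the software used. Section 1.9.1 describes automatic landmark placement and a composite analysis, and nowhere says that only the 17 listed points entered the measurements. Gnathion may have been placed and condylion-gnathion exported, in which case Table 3.7 contains a wrong word and section 1.9.1 is one point short. This stands as far as it goes: it means nobody can say from the text which distance was measured. It does not remove the conflict, because the stated definition is the operational one and the stated list agrees with it.

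Three stronger readings are tempting and are not supported.

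- A reader might infer that the trial did measure ramus height in place of mandibular length. That holds only if the written definition was followed. The documents also never call Co-Gn mandibular length or rank it above the other skeletal outcomes.
- A reader might infer that the nasolabial angle has the same fault, since no subnasale or columella point is listed. Table 3.7 defines it as "The angle formed by drawing a line tangent to the base of the nose and a line tangent to the upper lip". Tangents are drawn to the soft-tissue outline and need no listed landmark, so there is no contradiction.
- A reader might infer that Wits cannot be measured and that the sample size falls with it. The plane is unspecified, not contradicted: section 1.9.1 names the Wits analysis, and the figures that may show the plane are not available here. The sample size in section 1.2.2 uses a standard deviation from a previous study and is unaffected.

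**Conclusion.** The point holds for Co-Gn. Its label conflicts with its operational definition, and a landmark list that is complete by its own count supports the definition. One Objective 1 outcome of 16 is therefore not identifiable from the plan, and following the text yields a different anatomical distance from the one the label names. This should be settled before any Co-Gn result is reported.

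The conclusion rests on one convention, that Gn denotes gnathion. The geometric range of 1.64 to 2.18 rests on illustrative proportions and shows only that the two distances are not interchangeable. For Wits, the documents support a request for clarification and no more.

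**What to change.** First, check the software export and establish which distance was recorded as Co-Gn. Then:

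- **If condylion-gnathion is intended:** correct the definition in Table 3.7 and add Gnathion to section 1.9.1. If gnathion was already digitised, only the text changes. If it was not, place it on the existing coded T0 and T1 images and re-export the measure. That is about 21 + 20 = 41 images, assuming 21 enrolled and the one Twin Block dropout reported in section 1.6.3.1 without a T1 film.
- **If condylion-gonion is intended:** rename the outcome Co-Go in Tables 3.7 and 3.11 and draw no condylion-gnathion (mandibular-length) conclusion from it.

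In either case, add to section 1.9.2 the points that define the occlusal plane for Wits, and state that the same construction is used at T0 and T1.

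The cost is small: no new radiographs, and at most one extra point per image by the same tracer under the existing coding. If gnathion has to be added and reliability is to be shown for it, the section 1.9.3 exercise must be repeated for that measure. That means 20 images traced twice by the principal investigator, two weeks apart, and once by the reference orthodontist: 20 × 3 = 60 single-point placements.
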